### 7.3.2 SERIOUS AR/AES

All SAEs and SUSARs should be reported on the day of occurrence, where these occur within 28 days of vaccination. The SAE form asks for nature of event, date of onset, severity, corrective therapies given, outcome and causality (i.e. unrelated, unlikely, possible, probably, definitely). The responsible investigator should sign the causality of the event. Additional information should be sent to the CI within 5 days if the reaction has not resolved at the time of reporting. Any expected SAR will also be reported via the MHRA yellow card system.

**SAEs:** An SAE/SUSAR form should be completed and emailed to the study CI immediately, who will in turn inform the JRCO (email to [[contact]](mailto:[contact])) within 24 hours.

**SUSARs:** All SUSARs will be reported by the CI to the relevant Competent Authority (MHRA) and to the REC and other parties as applicable. For fatal and life-threatening SUSARs, this will be done no later than 7 calendar days after the Sponsor or delegate is first aware of the reaction. Any additional relevant information will be reported within 8 calendar days of the initial report. All other SUSARs will be reported within 15 calendar days.

## 8. DATA MANAGEMENT

### 8.1 DATA COLLECTION

The following data will be collected:

- Patient demographics
- Current health to establish safety of immunisation
- Vaccination history:
  - previous exposure to influenza vaccine
  - previous reactions to vaccines
- Past medical history:
  - Medical indication for influenza vaccination or routine
  - Current Medication

### 8.2 DATA RECORDS

Paper records will be maintained at St Mary's Hospital (Imperial College Healthcare NHS Trust) of all participants enrolled in the study. Data will be collected by paper CRF. The clinical data will then be transferred to Public Health England via a UK government 'GSI gateway' secure server, which will include the patient's study number, date of birth, gender and initials, but no other identifiable information. Specific consent to share this patient identifiable information with Public Health England will be included on the study consent form.

These data will be entered into a study specific database according to local SOPs at PHE, Colindale, and linked to laboratory data as this becomes available. Clinical data will be verified electronically by a second study team member at St Mary's Hospital (Imperial College Healthcare NHS Trust), in order to monitor for completion errors or omissions.

Study data will be kept for 10 years following the child's 18th birthday, and then disposed of securely. Local paperwork will be kept as part of the patient notes/CRF as per local policy.

## 9. STATISTICS AND DATA ANALYSIS

Full details will be given in the statistical analysis plan produced by the Immunisation Department Statistician.

Primary analysis: As this is a small pilot study analysis of the measured outcomes is descriptive. Proportions with detectable shedding on each day by strain will be given with 95% confidence intervals as will area under the curve be given with 95% CIs. The median day of peak shedding will be calculated by strain as well as the range. Quantitative results for each individual who sheds will be plotted.

Secondary analysis: Antibody responses will summarised as geometric means and geometric mean ratios with 95% confidence intervals as well as proportions above assay thresholds (with 95% CIs). The relationship with shedding by strain assessed by plotting AUC against antibody titre (within those that do shed) and calculating the R-squared value as well as the regression coefficient in a linear regression model on logged data. This will require at least 10 shedding individuals. The relationship with any shedding will be assessed by calculating the geometric mean ratio (with 95% CI) in titres between those who do and do not shed.

Additional analyses: Relationships between shedding of each strain (cross tabulations showing those who shed both, one, neither). Comparisons to shedding to previous studies will be informal and based on comparing the point estimates 95% confidence intervals.

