Based upon in vitro studies, the manufacturer of LAIV (MedImmune) have stated that reduced replicative fitness of the A/H1N1pdm09 strain is likely to be the important root cause. However, this factor alone cannot explain the difference in effectiveness observed between the USA and sites elsewhere including the UK. This suggests that there is an important additional factor(s) involved. The US programme has been running for many more years than the UK – and in addition children 6 months to 24 months of age are offered IIV, unlike the UK. These prior vaccine exposures are potential contributory factors, which is currently being analysed by a group at Public Health England from a study conducted in 2017/18 for which [name] was CI.

LAIV shedding studies in children could be an important way to confirm whether impediments to viral replication do indeed explain these observed reductions in VE and what future implications (if any) this might have for the UK paediatric LAIV programme. LAIV virus replication in children will be dependent on virological and host factors. The virus factors include replicative fitness of individual strains and the

susceptibility to inhibition by other replicating strains (ability to compete). Host factors which may influence this include pre-existing specific immunity as a result of prior infection or previous vaccination (with either LAIV or IIV), and innate immune factors including mucosal immunity.

There is significant variability in shedding across viral subtypes in studies done to date, so there is a need to obtain local data in a small pilot observational study which will look in detail at virus shedding by sequential daily virus samples, something not possible on a larger scale. The data generated will inform future LAIV studies in the UK in terms of optimum time of sample collection for viral shedding studies, which are likely to be required on a regular basis, to supplement field studies of vaccine effectiveness. Obtaining additional samples (blood, oral fluids, nasal swabs) which are correlates of vaccine take will allow us to measure the association between type-specific vaccine immunogenicity and virus shedding and will add to existing data from previous seasons on this.

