## 1.2 RESEARCH QUESTION

To measure type-specific vaccine virus shedding by sequential daily virus samples, and assess how this relates to immunogenicity in the 2018/19 vaccination season.

This study will enrol up to 30 children that will allow these factors to be assessed. Both written informed consent from parent/ guardian and written assent from the child will be in place prior to any study procedure. All participants will have a baseline assessment of pre-existing influenza immunity (blood test, oral fluid collection and nasal swabs), followed by a single dose of LAIV. Parents will then be asked to take nasal swabs at home on days 1, 2, 3, 4, 5, 6, 7, 8, with further nasal swab, blood test and oral fluid collection in hospital 4 weeks later, in order to assess for immune responses to LAIV.

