#### 9.1.2. SECONDARY STUDY OUTCOMES

Quantitative analysis of immunogenicity using a range of indicators, including:

1. MN and HAI titres at each time point (day 0, 28) as well as ratios day 28/day0 and proportions above thresholds and seroconverting.
2. Equivalent data with matching HAI (oral fluid) samples
3. Nasal IgA responses to LAIV taken at the same time

...to measure the association between type-specific vaccine immunogenicity and virus shedding.

---

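### Shedding is related to an antibody titre of unstated time point with no day-0 term, so the crude association may misstate the link between shedding and vaccine response

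*Combined protocol and SAP*

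**What the plan says.** The secondary analysis in section 9 has two parts that link antibody to shedding, each done by strain.

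- **Amount shed.** The plan is "plotting AUC against antibody titre (within those that do shed", then "calculating the R-squared value as well as the regression coefficient in a linear regression model on logged data". A size condition follows: "This will require at least 10 shedding individuals".
- **Any shedding.** The plan is "calculating the geometric mean ratio (with 95% CI) in titres between those who do and do not shed".

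Neither part says whether the titre is the day-0 value, the day-28 value or their ratio, and neither names a covariate. Section 9.1.2 lists "MN and HAI titres at each time point (day 0, 28) as well as ratios day 28/day0" among the outcomes, with the stated purpose "to measure the association between type-specific vaccine immunogenicity and virus shedding". It does not say which of these quantities enters the two analyses of section 9.

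On prior immunity, section 1.1 states: "Host factors which may influence this include pre-existing specific immunity as a result of prior infection or previous vaccination". Section 1.2 states: "All participants will have a baseline assessment of pre-existing influenza immunity". Section 9 leaves full details to a separate statistical analysis plan, which is not in the text available for review.

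**The concern.** The secondary objective is to relate the response to the vaccine to shedding. A child who arrives with a high titre may shed less because of it, and may still have a high titre four weeks later for the same reason. If so, a crude comparison of day-28 titres mixes two things: how prior immunity affects shedding, and how shedding goes with the response. The first pulls the association down and can offset the second.

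Using the day 28/day 0 ratio is not a clean escape. If titres rise less from a high baseline, children with low day-0 titres show larger rises whether or not they shed, and the ratio errs the other way. A confidence interval does not reveal either error, because both are bias and not imprecision. The direction of the reported association could then depend on a choice of time point that the plan leaves open.

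**Working it through.** **The plan's own figure.** Section 9.2 expects about 4-15 shedders per strain from 20-30 children. The earlier shedding rates are not given. Pairing low with low and high with high gives 20 × 0.20 = 4 and 30 × 0.50 = 15, so rates of about 20% to 50% (back-solved, an assumption). With 30 children, the binomial chance of at least 10 shedders is 0.06 at 20%, 0.64 at 35% and 0.98 at 50%.

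**Algebra.** Scale shedding and log day-0 titre to unit SD, and put log day-28 titre in the same units as day-0 titre. Suppose

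day-28 = γ × shedding + c × day-0 + error,

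where γ is the slope at fixed baseline, c the carry-over, and ρ the correlation of day-0 titre with shedding. Then:

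- crude day-28 slope = γ + cρ
- crude fold-rise slope = γ + (c - 1)ρ
- slope adjusted for day-0 titre = γ

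The documents give none of these values. Assume γ = 0.30 and c = 0.6 or 0.8.

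| ρ | Day-28 slope, c = 0.6 | Day-28 slope, c = 0.8 | Fold-rise slope, c = 0.6 | Fold-rise slope, c = 0.8 |
|---|---|---|---|---|
| -0.2 | 0.30 - 0.12 = 0.18 | 0.30 - 0.16 = 0.14 | 0.30 + 0.08 = 0.38 | 0.30 + 0.04 = 0.34 |
| -0.5 | 0.30 - 0.30 = 0.00 | 0.30 - 0.40 = -0.10 | 0.30 + 0.20 = 0.50 | 0.30 + 0.10 = 0.40 |
| -0.7 | 0.30 - 0.42 = -0.12 | 0.30 - 0.56 = -0.26 | 0.30 + 0.28 = 0.58 | 0.30 + 0.14 = 0.44 |

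In a one-predictor regression the sign is that of the covariance, so the sign of the crude slope is the same whichever of AUC and titre is treated as the outcome.

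**Check on the geometric mean ratio (GMR).** A simulation used a different set of assumptions: day-0 log2 titre with SD 2; log-odds of shedding falling by k per two-fold higher day-0 titre; day-28 log2 titre = λ × day-0, plus 1 if shedding, plus error with SD 1; 50% shedding. The true effect is a GMR of 2.0. Entries are for λ = 1.0 / 0.7 / 0.4.

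| k | Crude day-28 GMR | Fold-rise GMR | Adjusted GMR |
|---|---|---|---|
| 0 | 2.0 / 2.0 / 2.0 | 2.0 / 2.0 / 2.0 | 2.0 |
| 0.25 | 1.04 / 1.26 / 1.54 | 2.00 / 2.43 / 2.96 | 2.0 |
| 0.5 | 0.64 / 0.89 / 1.26 | 2.00 / 2.82 / 3.97 | 2.0 |
| 1.0 | 0.37 / 0.61 / 1.02 | 2.00 / 3.30 / 5.48 | 2.0 |

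The fold-rise ratio is right only when λ = 1 or when shedding does not depend on baseline. With 30 children, k = 0.5 and λ = 0.7, the crude GMR falls below 1 in 61% of simulated trials, against 1% after adjustment. The SD of the log2 GMR is 0.61 crude and 0.42 adjusted. At k = 1.0 and λ = 0.4, adjustment costs precision (0.44 crude, 0.49 adjusted).

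**Check on the regression among shedders.** With a true slope of 0.5 the crude slope ran from 0.50 to -0.50 over the assumed range, and the adjusted slope was 0.49 to 0.50. With 10 shedders and no confounding at all, the crude slope was still negative in 14% to 26% of samples, so imprecision is a separate and serious limit there.

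**The case against.** **The titre may be the day-0 one.** Section 9 does not say. If day 0 is meant, the analysis describes prior immunity as a predictor of shedding and this confounding does not arise. That stands. But section 9 would then contain no analysis of vaccine response against shedding, which is the stated objective. The time point has to be fixed on either reading.

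**The day-0 titre is used.** A reader might infer that it is collected and ignored. The documents do not support that: section 9.1.2 lists day-0 titres, day 28/day 0 ratios and seroconversion. What is missing is a day-0 term in the shedding analyses. Reporting the association for both the day-28 titre and the ratio would bracket the fixed-baseline slope when ρ is negative and carry-over lies between 0 and 1. Section 9 does not promise both, and does not say which would count.

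**The premises are assumed.** Section 1.1 says that prior immunity may influence replication and gives no direction. Carry-over into the day-28 titre is general reasoning. This stands and limits the verdict.

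**It is a descriptive pilot.** Section 9.2 says that the study is not powered for significance testing, and a crude association is a legitimate description. Bias here is relative to the association at a given baseline. Yet section 9.2 also gives the relationship between shedding and immunogenicity as a design aim, and an unadjusted figure is easily read as being about response.

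**A fuller plan is promised.** It may add the adjustment, which cannot be checked here. The written text does not.

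**Conclusion.** The point holds in a conditional form. As written, the two shedding analyses name no titre time point and have no day-0 term. If the day-28 titre is meant, and if prior immunity lowers shedding and carries into the day-28 titre, the crude association is too low; the ratio is too high whenever carry-over is below 1. On the assumed values the error runs from mild attenuation (0.14 to 0.18 against 0.30 at ρ = -0.2) to a reversed sign (-0.12 to -0.26 at ρ = -0.7).

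A reader might infer that the association will be hidden or reversed. The documents do not support that: they give no correlation, carry-over or effect size, and with no dependence of shedding on baseline there is no bias. Nor does the point call for moving the AUC analysis from shedders to all vaccinated children, which is a separate choice. It affects how a secondary association is interpreted; the primary outcome is untouched. The change is worth making because it is cheap and its covariate is already planned.

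**What to change.** In section 9 or the fuller statistical analysis plan:

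1. State the time point of the titre in each shedding analysis.
2. For each strain, report the shedder/non-shedder GMR of day-28 titre adjusted for log day-0 titre, with 95% CI, beside the crude GMR.
3. Keep the AUC regression in shedders and, where there are at least 10, add log day-0 titre. Give the coefficient with its 95% CI and say that it will be imprecise.
4. Report separately how day-0 titre relates to shedding, which addresses the question of prior immunity directly.
5. Use the same form for oral fluid and nasal IgA where both time points exist.

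No new data are needed. The cost is one covariate and possible loss of precision with 4-15 shedders per strain: at 10 shedders the residual degrees of freedom fall from 10 - 2 = 8 to 10 - 3 = 7. Two limits should be noted. Serum titre may not capture mucosal immunity. Sections 6 and 6.1.1 also allow the baseline blood up to 2 months before vaccination, so the covariate is not always a true day-0 value.

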### 9.1.3. OTHER STUDY OUTCOMES

Relationships between shedding of each strain (cross tabulations showing those who shed both, one, neither).

To compare how type-specific vaccine virus shedding in 2018/19 differs from previous studies in 2016/17/18 (conducted by this group, Eudract 2013-003592-35, 2016-002352-24, 2017-000952-24) following change in the A/H1N1pdm09 vaccine virus strain.

In an exploratory analysis, to cell-mediated immunity (CMI) will be correlated to the above primary and secondary endpoints, where available.

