## 9.2 SAMPLE SIZE ESTIMATION

This is a small pilot study to assess virus shedding by sequential daily virus samples in children following LAIV administration, something not possible on a larger scale. The study is not powered for significance testing, but is designed to measure the timing of shedding and relationships between shedding and immunogenicity outcomes. Based on shedding rates in previous studies, and assuming more time points will detect more shedding then a sample size of 20-30 participants should provide approximately 4-15 individuals shedding each strain for whom the kinetics of shedding can be assessed. This, in combination with data on larger numbers with samples at days 1,3 and 6 will help determine the optimum timing of sampling.

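### The cross-season shedding comparison sets separate 95% intervals side by side and never estimates the between-season difference or its uncertainty

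*Combined protocol and SAP*

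**What the plan says.** Section 9.1.3 (Other study outcomes) states the aim: "To compare how type-specific vaccine virus shedding in 2018/19 differs from previous studies in 2016/17/18", "following change in the A/H1N1pdm09 vaccine virus strain". It lists three earlier studies by the same group.

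Section 9 (Additional analyses) gives the method: "Comparisons to shedding to previous studies will be informal and based on comparing the point estimates 95% confidence intervals". It mentions no difference or ratio between seasons, and no rule for reading the intervals.

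Section 9 also says "As this is a small pilot study analysis of the measured outcomes is descriptive", and section 9.2 says "The study is not powered for significance testing". Section 9 leaves full detail to a separate statistical analysis plan, which is not in the text reviewed.

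**The concern.** The aim is a contrast between seasons, but the method reports only each season's own estimate and interval. A reader who wants to know how large a change the data support, or which changes they exclude, has to judge that by eye from two intervals, neither built for the purpose.

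The comparison bears on a hypothesis that section 1.1 names, reduced replicative fitness of the A/H1N1pdm09 vaccine strain. With 20-30 children the 2018/19 interval will be wide, so the way the pair is read matters.

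The omission also stands out within the plan. For antibody titres, section 9 already gives geometric mean ratios with 95% intervals, including the ratio between children who do and do not shed. Only the cross-season comparison has no direct contrast.

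**Working it through.** **Inputs from the protocol.** Each estimate has a 95% interval (section 9: "Proportions with detectable shedding on each day by strain will be given with 95% confidence intervals"). On size, section 9.2 says "a sample size of 20-30 participants should provide approximately 4-15 individuals shedding each strain". The previous rates behind 4-15 are not given, so that figure cannot be derived independently. It is consistent with 4/20 = 20% and 15/30 = 50%.

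**Assumptions.** The earlier studies' sizes and rates are not in the documents. Earlier n is taken as 30 to 400 and the earlier proportion as 20%. A 2018/19 proportion of 45% lies within the implied 20-50% and means 0.45 × 30 = 13.5 shedders.

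**A single example.** Take 15/30 now and 25/100 earlier.
- Wilson interval: [p + z²/2n ± z√(p(1−p)/n + z²/4n²)] / (1 + z²/n), with z = 1.96.
- Now: 0.332 to 0.668. Earlier: 0.175 to 0.343. They overlap.
- Newcombe lower limit for the difference: 0.25 − √[(0.500 − 0.332)² + (0.343 − 0.250)²] = 0.25 − 0.192 = 0.058.
- Newcombe upper limit: 0.25 + √[(0.668 − 0.500)² + (0.250 − 0.175)²] = 0.25 + 0.184 = 0.434.

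The planned output would show two overlapping intervals. It would not show that the difference is 25 points with a 95% interval of about 6 to 43.

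**Why calibration fails.** With no true change, the standard errors s₁ and s₂ are proportional to 1/√30 and 1/√100.
- Non-overlap requires |d| > 1.96(s₁ + s₂). Its approximate error rate is 2[1 − Φ(1.96 × (s₁ + s₂)/√(s₁² + s₂²))] = 2[1 − Φ(1.96 × 1.357)] = 0.8%.
- Checking the earlier point estimate against the 2018/19 interval ignores s₂. Its approximate error rate is 2[1 − Φ(1.96 × s₁/√(s₁² + s₂²))] = 2[1 − Φ(1.96 × 0.877)] = 8.6%.

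One reading is far stricter than 5% and the other looser.

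**Exact enumeration over both binomials, 30 children in 2018/19.** Each cell is the probability that the rule indicates a change.

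| True proportions (earlier, now) | Earlier n | Newcombe interval excludes 0 | Wilson intervals do not overlap | Exact intervals do not overlap | Earlier point outside 2018/19 Wilson interval |
|---|---|---|---|---|---|
| 20%, 20% | 100 | 4.8% | 0.7% | 0.4% | 8.9% |
| 20%, 45% | 60 | 69% | 39% | 30% | 83% |
| 20%, 45% | 100 | 77% | 50% | 40% | 85% |
| 20%, 45% | 200 | 83% | 63% | 53% | 86% |
| 20%, 45% | 400 | 86% | 72% | 62% | 87% |

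With exact instead of Wilson intervals, the point-estimate reading flags 5.5% under no change at earlier n = 100, and 13.1% at earlier n = 30. How far it over-calls therefore depends on the interval type and on the earlier n.

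**What the difference interval does not cure.** For a true change from 20% to 40% with 30 children now, it excludes zero 39, 52, 60 and 67% of the time at earlier n = 30, 60, 100 and 200. It still misses the change 33-61% of the time.

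**Swab days.** This study swabs on days 1 to 8. Section 9.2 refers to use "in combination with data on larger numbers with samples at days 1,3 and 6", and itself assumes that more time points detect more shedding. It does not say outright that those data are the earlier-season studies. If they are, a proportion with any shedding is not comparable. With independent daily detection of 5-10% (a simplification), identical shedding gives 1 − 0.95³ = 14% to 1 − 0.90³ = 27% from three swabs, but 1 − 0.95⁸ = 34% to 1 − 0.90⁸ = 57% from eight.

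**The case against.** A reader might infer that a real change in shedding is likely to be reported as no difference. The documents do not support that.
- The plan states no overlap rule. It names point estimates as well as intervals, and checking one season's point estimate against the other's interval can err towards over-calling change.
- Even under an overlap reading, a change from 20% to 45% is shown more often than not at an earlier n of 200 or 400 (53-63% and 62-72%).
- Much of the insensitivity comes from 20-30 children and would survive any change of method.

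It can also be said that the comparison is openly informal, sits below the primary and secondary outcomes, and belongs to a descriptive pilot whose sample size does not depend on it. The separate analysis plan might already specify a difference. And an interval around a contrast between eight swab days and three could lend false precision to a false increase.

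All of this stands as a limit on the size and direction of the harm, and the swab-day point shapes the fix. It does not remove the gap. However the intervals are read, the quantity in section 9.1.3 has no interval of its own. Descriptive status is no bar, because a difference with an interval is estimation, and section 9 already does the equivalent for titres.

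**Conclusion.** The concern holds in a limited form. The plan asks how shedding differs between seasons but does not estimate the uncertainty of that difference. With 30 children now and 100 earlier, the plausible readings of side-by-side intervals range from 0.4% to 8.9% false indication under no change, and from 40% to 85% indication of a change from 20% to 45%. A difference interval gives 4.8% and 77%. These figures rest on assumed earlier sizes and rates and on reading rules the plan does not state, so neither the size nor the direction of the error in practice can be fixed from the documents. The consequence is modest, but the remedy is cheap enough that the change should be made.

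**What to change.** In section 9 (Additional analyses), or in the separate analysis plan, replace the side-by-side comparison with the following, by strain and above all for A/H1N1pdm09:
- the difference in proportion shedding between 2018/19 and each earlier study, with its own 95% interval (Newcombe);
- the difference in mean log viral load, with its own 95% interval;
- both restricted to swab days common to the studies compared.

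Add a sentence that neither overlap of the separate intervals nor a difference interval that includes zero will be taken as evidence of no change. No p-values are needed, and the comparison stays descriptive.

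Cost: a few sentences and a little more analysis, with no new participants or samples. The day-specific counts that would give separate intervals are enough for the proportions, and the same group ran the earlier studies. Days not shared with those studies drop out of this one comparison but stay in the primary analysis. The limited sensitivity from 20-30 children is unchanged.
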